## CHAPTER 3: METHODOLOGY

### Description of Methodology

#### 3.1 Study Design

Prospective open-label study on patients with pleural infection who were given either pleural irrigation or intrapleural t-PA and DNase from **June 2023 – June 2025** in Universiti Kebangsaan Malaysia (UKM) Medical Center

#### 3.2 Study Population

Adult patients with pleural infection (complex pleural effusion or empyema) with poor outflow ( $\leq 150$  cc) from chest drain after 24 Hours of insertion in medical and non-medical wards UKMMC

#### 3.3 Sample size and Power of Study

By using power and sample size programme calculator :

Prior data indicate that the failure rate among controls is 0.15. If the true failure rate for experimental subjects is 0.32, we will need to study 39 experimental subjects and 39 control subjects to be able to reject the null hypothesis that the failure rates for experimental and control subjects are equal with

probability (power) 0.8. The Type I error probability associated with this test of this null hypothesis is 0.5. We will use a continuity-corrected chi-squared statistic or Fisher's exact test to evaluate this null hypothesis.

N = 39+/-4 (IPFT with alteplase and DNase) and 39+/-4 (pleural irrigation with normal saline)

Study used as a reference :

Pleural irrigation trial (PIT): a randomised controlled trial of pleural irrigation with normal saline versus standard care in patients with pleural infection Clare E. Hooper, Anthony J. Edey, Anthony Wallis, Amelia O. Clive, Anna Morley, Paul White, Andrew R.L. Medford, John E. Harvey, Mike Darby, Natalie Zahan-Evans and Nick A. Maskell,

Reference for sample size taken from the primary outcome of this research in which patients receiving saline irrigation had a significantly greater reduction in pleural collection volume on computed tomography compared to those receiving standard care (median (interquartile range) 32.3% (19.6–43.7%) reduction versus 15.3% (–5.5–28%) reduction) (  $p < 0.04$ ).

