### 2.2 Primary Objective:

- To measure the volume of pleural effusion drainage (in mls) 48 hours following randomization

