### Medication Regimen :

t-PA (Alteplase) 5mg and DNase (Pulmozyme)5mg

t-PA (Alteplase) that is available in our pharmacy is 50mg ampoule and DNase (Pulmozyme) is 2.5mg per ampoule

The number of installation of intrapleural t-PA/DNase depends on the discretion of the treating physician (at least 6 hours apart between each dose). 5mg of Alteplase (t-PA) and 5mg DNase are diluted in each 50ml of 0.9% sodium chloride solution. t-PA and DNase are not mixed together in one syringe. The detailed method of t-PA/DNase therapy administration is described in Appendix 1. In brief, both medication are administered sequentially which t-PA is first instilled intrapleurally and the chest tube is then clamped for 45 minutes, then unclamped to allow free drainage for 45 minutes. The same procedure is then repeated for DNase. Selection of the timing of treatment and removal of chest tube are depending on the chest physician's judgement.

However, as for patients who were randomized into pleural irrigation group, subjects were administered 250 ml of 0.9% sodium chloride via chest tube a three way tap from a drip stand which were allowed drainage freely over 1 hour. Pleural irrigation will be performed minimum of 3 installations and maximum of 9 installation (3 times per day).

Both groups received standard care of treatment : which includes regular flushing of chest drain to maintain patency using 20mls of normal saline.

The primary outcome was to evaluate the volume of pleural effusion drainage (in mls) 72 hours following randomization. The volume drained measured after subtracting the amount of volume administered as per protocol.

The secondary outcome are measured by the change in the area of pleural opacity in chest x-ray (day 7 post t-PA/DNase compared to baseline), measured as the percentage of the ipsilateral hemithorax occupied by effusion. The area of pleural opacity and the area of the ipsilateral hemithorax will be measured digitally by two radiologists using Horos Project Software, v3.2.1 as described previously in Multicentre Intrapleural Sepsis Trial 2 (MIST-2)

Other outcomes that will be monitored include :

1. Inflammatory markers including serum C-reactive protein (CRP) & white blood count
2. Length of hospital stay in days
3. The need of surgical intervention within 30 days
4. Adverse effects :
  - a. Chest pain required escalation of analgesics
  - b. Systemic bleeding
  - c. Pleural bleeding

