During any point of treatment subjects will be allowed to cross-over and analysis will be done as per intention to treat. Subjects in the pleural irrigation group may be switched to IPFT group if there is poor response to treatment (poor drainage of effusion), or adverse effects of irrigation as per clinician's judgement. On the contrary, subjects in the IPFT group may be switched to pleural irrigation group if patient developed any adverse effects of IPFT (e.g hemothorax, haemoptysis). Those who failed both treatment will be referred for surgical intervention

Monitoring Parameters :

a. Pleural irrigation group

Parameter	Day0	Day1	Day2	Day3	Day7	Day30
Investigations						

 
• Full blood count (FBC)               
 
○ WBC
 
○ Hemoglobin
 
 
 
	√	√	√	√	√	
• C- reactive protein (CRP)	√				√	
• Chest X-ray	√				√	
• Ultrasound Thorax	√	√	√	√		
Adverse effects						
• Chest pain required escalation of analgesics		√	√	√		
• Gastrointestinal bleed		√	√	√		
• Bleeding from chest drain site		√	√	√		
• Intrapleural hemorrhage		√	√	√		
• Hemoptysis		√	√	√		
• Clinical deterioration – hypotension, dyspnea		√	√	√		
• Hb drop >10% required transfusion blood		√	√	√		
• Death related to intrapleural saline irrigation		√	√	√		

Others Outcome						
• Mortality						
• Surgical intervention						

b. IPFT group

Net Volume of pleural fluid drained (ml) post pleural irrigation	Baseline	Day 1	Day 2	Day 3
	√	√	√	√
Cumulative pleural fluid drained post pleural irrigation				√

b. Intrapleural fibrinolytic group

Parameter	Day0	Day1	Day2	Day3	Day7	Day30
Investigations						
• Full blood count (FBC) 
 
○ WBC
 
○ Hemoglobin
 
	√	√	√	√	√	
• C- reactive protein (CRP)	√				√	

• Chest X-ray	√				√	
• Ultrasound Thorax	√	√	√	√		
Adverse effects						
• Chest pain required escalation of analgesics		√	√	√		
• Gastrointestinal bleed		√	√	√		
• Bleeding from chest drain site		√	√	√		
• Intrapleural hemorrhage		√	√	√		
• Hemoptysis		√	√	√		
• Clinical deterioration – hypotension, dyspnea		√	√	√		
• Hb drop >10% required transfusion blood		√	√	√		
• Death related to intrapleural therapy		√	√	√		
Others Outcome						
• Mortality						
• Surgical intervention						

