Net Volume of pleural fluid drained (ml) post IPFT	Baseline	Day 1	Day 2	Day 3
	√	√	√	√
Cumulative pleural fluid drained post IPFT				√

[figure not shown]
Operational Definition:

[figure not shown]
- Treatment success: significant amount of pleural drainage post intervention, reduction of opacity on chest x-ray and resolution of inflammatory markers on day 7 without surgical intervention within 30days
- Treatment failure:
  - Poor drainage from chest drain, failure of resolution of pleural effusion or empyema at least 50% reduction on opacity on chest x-ray and clinical evidence of ongoing infection that requires surgical intervention within 30days post randomization or death before discharge.

All patients will be followed up in respiratory clinic day 30 after discharge or phone call if patient defaulted clinic appointment.

Data will be collected prospectively (Appendix 5) by reviewed patient demographics, clinical data on length of hospital stay, pleural fluid analysis, intrapleural therapy, radiographic characteristics, adverse events, Laboratory data (blood leukocyte count, C-reactive protein, haemoglobin level), Intrapleural therapy data including number of chest tubes, duration of chest tube in pleural cavity and cumulative volume of pleural fluid drained. Besides that, length of hospital stay, treatment outcomes, surgical interventions and the occurrence of complications are recorded.

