### 3.7 Study protocol /flow chart

### 3.7 Statistical Analysis

Statistical analysis will be performed using the available SPSS software version 19. All numerical data will be subjected to normality testing using Shapiro-Wilk test. All normally distributed data will be expressed as mean  $\pm$  standard deviation (SD) whereas non-normally distributed data were expressed as median (IQR). For normally distributed data, parametric test with Student's t-test will be used. For non-normally distributed data, the Mann-Whitney test will be used or equivalent nonparametric tests. Within groups, the Wilcoxon rank sum test will be used. For qualitative data, Chi-Square test and Fisher's Exact test will be used. The significant p-value will be taken as  $<0.05$  or in the case of multiple comparisons it will be adjusted with a Bonferonni correction.

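### The 39 per arm rests on two median CT-volume reductions used as failure rates at a Type I error of 0.5, so the stated 80% power does not apply to the primary outcome in mL

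*Combined protocol and SAP*

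**What the plan says.** Section 3.3 (Sample size and Power of Study) compares two failure rates: "Prior data indicate that the failure rate among controls is 0.15. If the true failure rate for experimental subjects is 0.32". It asks for 39 patients per arm (written as 39 ± 4) for a power of 0.8, to be tested by a continuity-corrected chi-squared statistic or Fisher's exact test. On the error rate it says: "The Type I error probability associated with this test of this null hypothesis is 0.5". It then says that the reference for the sample size is the primary outcome of the cited irrigation trial, reported as "median (interquartile range) 32.3% (19.6–43.7%) reduction versus 15.3"%, for saline irrigation against standard care.

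The primary outcome of this trial is continuous. Section 2.2 has: "To measure the volume of pleural effusion drainage (in mls) 48 hours following randomization". Section 3.6, under Medication Regimen, has: "The primary outcome was to evaluate the volume of pleural effusion drainage (in mls) 72 hours following randomization", with the instilled volume subtracted. Section 3.7 (Statistical Analysis) plans Student's t-test for normally distributed data and adds: "For non-normally distributed data, the Mann-Whitney test will be used or equivalent nonparametric tests". It sets significance at p < 0.05.

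**The concern.** Four things do not fit together.

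- **Type of quantity.** The rates 0.15 and 0.32 equal the cited medians after rounding. A median percentage change is not a proportion of patients with an event, so a two-proportion formula does not apply. The better result (32.3%) also becomes the higher failure rate. That is a labelling error and does not alter a two-sided N.
- **Contrast.** The source compared saline with standard care. Its 32.3% does describe a saline arm, which is the comparator here, but section 3.3 assumes no value for t-PA/DNase. The effect under test is never specified.
- **Outcome and test.** The trial is sized for chi-squared or Fisher on a binary outcome, while the primary analysis is a t-test or Mann-Whitney on mL.
- **Error rate.** A Type I error of 0.5 contradicts the 0.05 of section 3.7.

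The only power statement in the protocol is therefore not about its primary comparison. A reader cannot tell what difference in drained volume the trial can detect, or whether a null result would be informative.

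**Working it through.** **1. Reproducing 39.** Inputs from section 3.3: p1 = 0.15, p2 = 0.32, power 0.8, equal arms. Two-sided is inferred from the null hypothesis of equal rates. Then Δ = 0.17 and the mean rate is 0.235.

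n0 = [z(1−α/2)·√(2 × 0.235 × 0.765) + 0.842·√(0.15 × 0.85 + 0.32 × 0.68)]² / 0.17²

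n = (n0/4)·[1 + √(1 + 4/(n0·Δ))]² (continuity correction)

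The two square roots in n0 are 0.5996 and 0.5874.

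- α = 0.5, z = 0.674: n0 = 27.96 and n = 38.83, so **39 per arm**, as printed.
- α = 0.05, z = 1.960: n0 = 96.46 and n = 107.91, so **108 per arm**.

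No variant tried at 0.05 (one- or two-sided, corrected or not, unpooled, arcsine) gives 39; they run from 74 to 108. The 0.5 therefore entered the calculation and is not only a misprint. A one-sided 0.25 would be numerically the same but is stated nowhere. On the plan's own rates, 39 per arm at two-sided 0.05 has a power of 0.32 by the continuity-corrected formula and 0.34 by exact Fisher. Swapping the two rates changes nothing.

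**2. What 39 per arm can detect on the primary outcome.** Two-sided 0.05, power 0.8.

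- *t-test.* The normal approximation is d = 2.802 × √(2/39) = 0.634. The exact noncentral-t solution is **0.643 SD** (0.679 at 35 per arm, 0.611 at 43).
- *Mann-Whitney (Noether's formula).* P = 0.5 + √(7.849/(6n)) = 0.5 + √(7.849/234) = **0.683**, the probability that a t-PA/DNase patient drains more than an irrigation patient (0.693 at 35, 0.674 at 43). A simulation with lognormal data at this P and 39 per arm gave a power of 0.81.

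**3. In mL, t-test only.** The documents give no SD in mL and no target difference, so both are assumptions here.

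| Assumed SD (mL) | Detectable at 39 per arm (0.643 × SD) | n per arm for an assumed 300 mL |
|---|---|---|
| 400 | 257 mL | 29 |
| 600 | 386 mL | 64 |
| 800 | 514 mL | 113 |

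This conversion does not carry over to the Mann-Whitney figure. A probability of 0.683 equals 0.67 SD under normality, but about 0.62, 0.54 or 0.47 SD for lognormal data with assumed log-SDs of 0.5, 0.8 or 1.0.

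**4. Cross-over.** Section 3.6 says: "During any point of treatment subjects will be allowed to cross-over and analysis will be done as per intention to treat". Section 3.3 makes no allowance for this. If cross-over shrank a difference of 0.643 SD by an assumed 10%, 20% or 30% (to 0.579, 0.514 or 0.450 SD), power at 39 per arm would be 0.71, 0.61 or 0.50, and 80% power would need 48, 61 or 79 per arm.

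**The case against.** The strongest defence is that the trial may have been sized on treatment failure, a binary outcome that section 3.6 does define, ending in "clinical evidence of ongoing infection that requires surgical intervention within 30days post randomization or death before discharge". This does not hold. Treatment failure is not the primary outcome, no prior rate for it is cited, and section 3.3 ties its inputs to CT volume.

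Several narrower objections do stand:

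- The protocol never says outright that medians were entered as proportions. This is an inference, though a strong one: both values match after rounding and the section names the source.
- Chapter 1 does give a figure for t-PA/DNase, a fall of about 50% in day-7 chest x-ray opacity. It concerns another outcome and a regimen with 16 mg of t-PA, and section 3.3 does not use it.
- Cross-over under intention to treat is a declared choice, and section 3.5 acknowledges that patients in whom irrigation fails will receive fibrinolysis. How much switching would fall within 48 or 72 hours is unknown, so the dilution figures are only illustrative.
- It has not been shown that 39 per arm is too few. If the true difference is about 0.64 SD or more, undiluted, it suffices for 80% power by t-test.

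**Conclusion.** The concern holds and must be fixed. The stated N and its 80% power come from invalid inputs and a Type I error of 0.5, and they say nothing about the primary outcome. At 0.05 the same inputs would give 108 per arm instead of 39. That gap measures the effect of the error rate alone; 108 is not a required N, and 0.32 to 0.34 is not the trial's actual power.

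For net mL drained, 39 per arm has 80% power for 0.64 SD by t-test, or for a Mann-Whitney probability of about 0.68, with two-sided 0.05 and no dilution by cross-over. Under the assumed SDs and the assumed 300 mL difference, 39 could be more or less than enough. The defect is a missing justification, not demonstrated underpowering.

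**What to change.** 1. Delete the two-proportion calculation in section 3.3, with its 0.8 power claim and the Type I error of 0.5. Changing 0.5 to 0.05 alone is not a remedy, because it would still power the wrong quantity.
2. Reconcile the primary time point (48 hours in section 2.2, 72 hours in section 3.6) first, since the SD depends on it.
3. Insert text such as: *For net volume drained (mL) at the reconciled time point, with two-sided alpha 0.05, 39 patients per arm give 80% power for a difference of 0.64 SD by t-test (0.68 at 35 per arm, 0.61 at 43), or by Mann-Whitney for a probability of about 0.68 that a patient given t-PA/DNase drains more than one given irrigation.*
4. Convert the t-test figure to mL over a range of SDs. The unit's fibrinolysis records since 2017 (end of Chapter 1) can inform the SD only if they hold drained volume. They would cover one arm and varying doses, and the text should say so.
5. State the mL difference judged worthwhile and the N it needs, set against 39.
6. State the cross-over expected and show the power with the difference diluted by it.

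The cost is a rewrite of one section, one decision on the time point and a check of the unit's records. Whether N must change cannot be judged until the worthwhile difference and the SD are stated.

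### The 39 per arm was calculated with a Type I error of 0.5; at the plan's own 0.05 threshold the claimed 80% power is about 32–34%

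*Combined protocol and SAP*

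**What the plan says.** Section 3.3 gives a complete set of inputs for comparing two proportions.

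- Control rate: "Prior data indicate that the failure rate among controls is 0.15".
- Experimental rate: "If the true failure rate for experimental subjects is 0.32".
- Sample size: "we will need to study 39 experimental subjects and 39 control subjects", later given a margin of 4 either way in each arm.
- Hypothesis and power: the aim is to "reject the null hypothesis that the failure rates for experimental and control subjects are equal with" "probability (power) 0.8".
- Type I error: "The Type I error probability associated with this test of this null hypothesis is 0.5".
- Test: continuity-corrected chi-squared or Fisher's exact.

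Section 3.7 (Statistical Analysis) sets a different threshold: "The significant p-value will be taken as $<0.05$ or in the case of multiple comparisons" a Bonferroni adjustment is applied. Nothing in the document explains the 0.5 or reconciles it with the 0.05.

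**The concern.** The two sections give Type I error rates that differ by a factor of ten. There are two possible explanations. Either 0.5 is a slip of the pen for 0.05 and the calculation behind it is sound, or 0.5 was the value entered in the sample-size program and 39 is the result of that entry. The first needs one digit changed. The second makes both the sample size and the stated power wrong.

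Section 3.3 is the only justification of the sample size in the document, so an ethics committee or reader has nothing else to rely on. If the power is overstated, a non-significant comparison of failure rates could be read as showing that the treatments perform alike, when the design had little chance of separating them on that measure.

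**Working it through.** **Inputs, all from section 3.3 unless noted.** p1 = 0.15, p2 = 0.32, power 0.80, 1:1 allocation, continuity-corrected chi-squared or Fisher's exact test, alpha 0.5. Section 3.7 gives alpha 0.05. Sidedness is not stated; I take two-sided because the null is equality of the two rates.

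**Formula.** With d = p2 − p1 and p̄ = (p1 + p2)/2, the uncorrected size per arm is

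m = [z(1−α/2)·√(2p̄(1−p̄)) + z(power)·√(p1(1−p1) + p2(1−p2))]² / d²

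and the continuity-corrected size is

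n = (m/4)·[1 + √(1 + 4/(m·d))]².

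Here d = 0.17, d² = 0.0289 and p̄ = 0.235. Then √(2 × 0.235 × 0.765) = 0.5996, √(0.1275 + 0.2176) = 0.5875, and z(0.80) = 0.8416.

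**Step 1: reproduce the plan's figure, alpha 0.5.** z = 0.6745.

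- m = (0.6745 × 0.5996 + 0.8416 × 0.5875)² / 0.0289 = 27.96
- n = (27.96/4) × [1 + √(1 + 4/(27.96 × 0.17))]² = 38.83, so **39 per arm**, which matches.

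**Step 2: the same inputs, alpha 0.05.** z = 1.960.

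- m = (1.960 × 0.5996 + 0.8416 × 0.5875)² / 0.0289 = 96.46, so 97 per arm
- n = (96.46/4) × [1 + √(1 + 4/(96.46 × 0.17))]² = 107.91, so **108 per arm** (216 in total)

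**Step 3: could any 0.05 calculation give 39?**

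| Alpha | Sides | Uncorrected | Corrected |
|---|---|---|---|
| 0.5 | two | 28 | **39** |
| 0.5 | one | 9 | 19 |
| 0.05 | two | 97 | 108 |
| 0.05 | one | 76 | 88 |

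No 0.05 variant comes near 39. Solving the corrected two-sided formula backwards for the alpha that gives 80% power at 39 per arm returns 0.497. Exact enumeration of Fisher's test at alpha 0.5 and 39 per arm gives 80.8% power, so the stated 0.8 has the same source.

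**Step 4: power at 39 per arm, two-sided 0.05.** Inverting the continuity correction gives an effective size of (n·d − 1)²/(n·d²) = (6.63 − 1)²/(39 × 0.0289) = 28.12. Then

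power = Φ[(0.17 × √28.12 − 1.960 × 0.5996)/0.5875] = Φ(−0.466) = 32.1%.

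Exact binomial enumeration gives:

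| Per arm | Fisher's exact | Corrected chi-squared |
|---|---|---|
| 35 | 29.2% | 29.2% |
| 39 | 33.7% | 33.5% |
| 43 | 37.2% | 35.6% |

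**Step 5: the difference 39 per arm can detect.** With the control rate at 0.15 and alpha 0.05, the corrected formula needs 39.6 per arm for 0.46 and 37.6 for 0.47. Exact Fisher power at 39 per arm is 80.4% for 0.46 and 82.8% for 0.47. The detectable rate is therefore about 0.46–0.47, not 0.32.

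**The case against.** The strongest objection accepts the arithmetic and disputes its reach. The primary outcome is a continuous drainage volume in ml (sections 2.2 and 3.6), to be analysed by t-test or Mann-Whitney, so 32–34% is not the power of the primary comparison. At 39 per arm and two-sided 0.05, a t-test has 80% power for a standardised difference of about 0.64. The documents give no standard deviation for drainage volume, so what that means in ml is unknown. The inputs are also doubtful: 0.15 and 0.32 match the median CT volume reductions of 15.3% and 32.3% that section 3.3 quotes from its reference trial. Those are not proportions of patients failing, and they compare saline irrigation with standard care.

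This stands as a limit on interpretation. The remark about a design unable to separate the treatments holds only for the binary contrast, and 108 per arm should not be taken as the size the primary outcome needs. It does not rescue section 3.3. Doubtful inputs and a mismatched endpoint are separate faults, and the document offers no other basis for 39.

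A smaller objection is that 32–34% depends on the test. At two-sided 0.05 an uncorrected chi-squared test would have about 42% power (43.5% by enumeration), and a one-sided uncorrected test about 55%. Neither is the test section 3.3 names, and both are far below 80%. Any Bonferroni adjustment would lower power further.

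**Conclusion.** The concern holds. The 0.5 was the working value in the calculation: it reproduces 39 per arm exactly, and 0.05 does not under any variant tried. On the plan's own rates and named tests at two-sided 0.05, 39 per arm gives 32–34% power instead of 80%, and roughly 28–37% over the stated range of 35 to 43. The planned size is 39/108 = 36% of what those inputs require.

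This rests on the stated rates being taken at face value and on a two-sided test. The two-sided reading is an inference, supported by the exact reproduction of 39; a one-sided alpha of 0.25 has the same critical value and gives the same 39, and is equally far from 0.05. The result concerns the binary calculation in section 3.3 and says nothing about power for drainage volume.

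**What to change.** In section 3.3:

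1. State the Type I error as 0.05, two-sided, in agreement with section 3.7. Changing the digit alone is not enough, because 39 per arm with 80% power would then still be false.
2. Remove the claim of 80% power for 0.15 versus 0.32. Report that 39 per arm gives about 32–34% for that contrast with the named tests, that 80% would need 108 per arm, and that 39 per arm reaches 80% only for about 0.15 versus 0.47.
3. If the total stays at 78, describe the failure-rate comparison as exploratory.
4. Say that these figures apply to the binary comparison only. Justifying the size for the primary drainage volume is a separate task and needs an assumed difference and standard deviation in ml, which the documents do not give.

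The cost of items 1 to 3 is a rewritten paragraph and a less favourable stated power. Correcting the statement needs no extra patients; enlarging the trial would be a separate decision.
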